# 10.2 **Off Study Criteria**

- a) Thirty days after the last dose of the investigational agent.
- b) Death
- c) Lost to follow-up
- d) Withdrawal of consent for any required observations or data submission.
- e) Enrollment onto another COG therapeutic (anti-cancer) study

# 11.0 STATISTICAL AND ETHICAL CONSIDERATIONS

# 11.1 Sample Size and Study Duration

A minimum of 4 patients will be enrolled in this study. The expected maximum number of evaluable patients required to estimate the MTD/RP2D is 24. Once the MTD or recommended Phase 2 dose has been defined, up to 6 additional patients with recurrent or refractory solid tumors without restrictions on heme evaluability may be enrolled to acquire PK data in a representative number of young patients (i.e. patients < 12 years old). Therefore, a maximum of 36 patients are expected to be enrolled which allows for 6 patients at each of 4 dose levels, 6 additional patients enrolled at the MTD/RP2D for PK analysis, and a 20% inevaluable rate. Review of the enrollment rate into previous COG new agent studies indicates that 1-2 patients per month are available, which will permit completion of the study within 18-36 months. An absolute maximum of 65 patients is anticipated in the unlikely scenario that each of 4 dose levels is expanded to 12 patients due to different classes of AEs, 6 additional patients are enrolled at the MTD for PK analysis, and a 20% inevaluable rate. The absolute maximum would require about 33-65 months for completion.

# 11.2 **Definitions**

11.2.1 Evaluable For Adverse Events

Any patient who receives at least one dose of the study drug(s) and/or who experiences a dose-limiting toxicity is considered evaluable for Adverse Events. In addition, for the dose-escalation portion during Cycle 1, patients must receive at least 85% of the prescribed dose per protocol guidelines and must have the appropriate toxicity monitoring studies performed to be considered evaluable for dose limiting toxicity. Patients who do not have DLT and are not considered evaluable for toxicity will be replaced.

- 11.2.2 Maximum Tolerated Dose
  - The MTD will be the maximum dose at which fewer than one-third of patients experience DLT (See Section 5.5) during Cycle 1 of therapy.

PAGE 1 FOR USAGE POLICY

ADVL1515

- In the unlikely event that two DLTs observed out of 6 evaluable patients are different classes of Adverse Effects (e.g. hepatotoxicity and myelosuppression), AND all of the following conditions are met, expansion of the cohort to 12 patients will be considered:
  - One of the DLTs does not appear to be dose-related
  - The Adverse Effects are readily reversible
  - The study chair, DVL statistician, DVL committee chair or vice chair, and IND sponsor all agree that expansion of the cohort is acceptable

If fewer than 1/3 of patients in the expanded cohort experience dose-limiting toxicities, the dose escalation can proceed.

• The DLTs observed in the pharmacokinetic (PK) expansion cohort will be counted towards the total number of DLTs observed at the MTD during the dose escalation portion of the study. If  $\geq 1/3$  of the cohort of patients at the MTD (during the dose escalation plus the PK expansion) experience DLT then the MTD will be exceeded.

# 11.3 **Dose Escalation and Determination of MTD**

The rolling six phase 1 trial design will be used for the conduct of this study. Two to six patients can be concurrently enrolled onto a dose level, dependent upon (1) the number of patients enrolled at the current dose level, (2) the number of patients who have experienced DLT at the current dose level, and (3) the number of patients entered but with tolerability data pending at the current dose level. Accrual is suspended when a cohort of six has enrolled or when the study endpoints have been met.

Dose level assignment is based on the number of participants currently enrolled in the cohort, the number of DLTs observed, and the number of participants at risk for developing a DLT (i.e., participants enrolled but who are not yet assessable for toxicity). For example, when three participants are enrolled onto a dose cohort, if toxicity data is available for all three when the fourth participant entered and there are no DLTs, the dose is escalated and the fourth participant is enrolled to the subsequent dose level. If data is not yet available for one or more of the first three participants and no DLT has been observed, or if one DLT has been observed, the new participant is entered at the same dose level. Lastly, if two or more DLTs have been observed, the dose level is de-escalated. This process is repeated for participants five and six. In place of suspending accrual after every three participants, accrual is only suspended when a cohort of six is filled. When participants are inevaluable for toxicity, they are replaced with the next available participant if escalation or de-escalation rules have not been fulfilled at the time the next available participant is enrolled onto the study.

The following table provides the decision rules for enrolling a patient at (i) the current dose level (ii) at an escalated dose level, (iii) at a de-escalated dose level, or whether the study is suspended to accrual:

# Pts	# Pts with	# Pts without	# Pts with	Decision
Enrolled	DLT	DLT	Data Pending	
2	0 or 1	0, 1 or 2	0, 1 or 2	Same dose level

CHILDREN'S ONCOLOGY GROUP

nstitute of the National Institutes of Health

THIS PROTOCOL IS FOR RESEARCH PURPOSES ONLY, SEE PAGE 1 FOR USAGE POLICY

2 0 0 2 De-escalate\* 3 0 0, 1 or 2 1, 2 or 3 Same dose level 3 1 0. 1 or 2 0.1 or 2 Same dose level 3 0 3 0 Escalate\*\* 3  $\geq 2$ 0 or 1 0 or 1 De-escalate\* 4 0 Same dose level 0, 1, 2 or 3 1, 2, 3 or 4 Same dose level 4 1 0, 1, 2 or 3 0, 1, 2 or 3 Escalate\*\* 4 0 4 0 De-escalate\* 4  $\geq 2$ 0, 1 or 2 0, 1 or 2 5 0 0, 1, 2, 3 or 4 1, 2, 3, 4 or 5 Same dose level 5 1 0, 1, 2, 3 or 4 0, 1, 2, 3 or 4 Same dose level Escalate\*\* 5 0 5 0 0, 1, 2 or 3 5  $\geq 2$ 0, 1, 2 or 3 De-escalate\* 0 6 0, 1, 2, 3, or 4 2, 3, 4, 5 or 6 Suspend 6 1 0, 1, 2, 3 or 4 0, 1, 2, 3 or 4 Suspend Escalate\* 6 0 or 1 5 or 6 0 or 1 0, 1, 2, 3 or 4 0, 1, 2, 3 or 4 De-escalate\* 6  $\geq 2$ 

\* If six patients already entered at next lower dose level, the MTD has been defined. \*\*If final dose level has been reached, the recommended dose has been reached.

If two or more of a cohort of up to six patients experience DLT at a given dose level, then the MTD has been exceeded and dose escalation will be stopped (see Section 11.2.2 for exception to rule).

In addition to determination of the MTD, a descriptive summary of all toxicities will be reported.

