## 4.1.7 Organ Function Requirements

A program funded by the National Cancer nstitute of the National Institutes of Health This protocol is for research purposes only, see page 1 for usage policy

- 4.1.7.1 Adequate Bone Marrow Function Defined as:
  - a. For patients with solid tumors without known bone marrow involvement:
    - Peripheral absolute neutrophil count (ANC)  $\geq 1000/\text{mm}^3$
    - Platelet count ≥ 75,000/mm^3 (transfusion independent, defined as not receiving platelet transfusions for at least 7 days prior to enrollment)
    - Hemoglobin  $\geq 8.0$  g/dl at baseline (may receive PRBC transfusions)
  - b. Patients with known bone marrow metastatic disease will be eligible for study provided they meet the blood counts in 4.1.7.1.a (may receive transfusions provided they are not known to be refractory to red cell or platelet transfusions). These patients will not be evaluable for hematologic toxicity. At least 5 of every cohort of 6 patients must be evaluable for hematologic toxicity for the dose-escalation part of the study. If dose-limiting hematologic toxicity is observed, all subsequent patients enrolled must be evaluable for hematologic toxicity.

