#### 5.3 **Dose Escalation Schema**

5.3.1 Inter-Patient Escalation

institute of the National Institutes of H

The starting dose of LY2606368 will be  $80 \text{ mg/m}^2$  (dose level 1) with dose levels for subsequent groups of patients as follows.

Dose Level	LY2606368 (mg/m²)
0	60
1*	80
2	100
3	125
4	150

\* Starting Dose Level

There will be no escalations beyond dose level 4 ( $150 \text{ mg/m}^2$ ), as previous pediatric Phase 1 studies have rarely defined a MTD greater than 160% of the adult MTD.

If the MTD has been exceeded at the first dose level, then the subsequent cohort of patients will be treated at a dose of  $60 \text{ mg/m}^2$  (dose level 0). If dose level 0 is not well tolerated, further de-escalation will not occur. The study will be closed to accrual.

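### Is it a flaw that the recommended dose can be declared at the top dose level on three to five patients without DLT, when a lower level needs six to be called the MTD?

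*Combined protocol and SAP*

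**What the plan says.** The decision table in Section 11.3 has the row "3 0 3 0 Escalate", and the rows for four and five patients with no DLT and nothing pending carry the same decision. The text of 11.3 says it in words: "if toxicity data is available for all three when the fourth participant entered and there are no DLTs, the dose is escalated". Section 5.3.1 sets the ceiling: "There will be no escalations beyond dose level 4". The double-asterisk footnote covers an escalation decision at that ceiling: "If final dose level has been reached, the recommended dose has been reached". The single-asterisk footnote belongs to de-escalation: "If six patients already entered at next lower dose level, the MTD has been defined".

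Three other places bear on the point.

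- Section 11.2.2 defines the MTD as the highest dose with DLT in fewer than one third of patients and gives no minimum number. It then adds: "The DLTs observed in the pharmacokinetic (PK) expansion cohort will be counted towards the total number of DLTs observed at the MTD". If the pooled proportion reaches one third, the MTD has been exceeded.
- Section 11.1 provides for the expansion: "up to 6 additional patients with recurrent or refractory solid tumors without restrictions on heme evaluability may be enrolled to acquire PK data".
- Section 4.1.7.1.b limits patients who are inevaluable for blood toxicity and adds: "If dose-limiting hematologic toxicity is observed, all subsequent patients enrolled must be evaluable for hematologic toxicity".

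**The concern.** Read side by side, the footnotes seem to apply two standards to one endpoint. A lower level needs six patients to be called the MTD, while the top level can be recommended on half as many. Below the ceiling, 0/3 is provisional: if the next level fails, accrual returns until six have been entered. At the ceiling nothing above can send accrual back. The top level is 150 mg/m², or 150/105 = 143% of the adult recommended dose. The expansion that follows is optional and has no restriction on hematologic evaluability, although neutropenia is among the agent's most frequent toxicities (Section 2.3.1). The MTD or recommended Phase 2 dose is a primary aim, so what would be at stake is the precision behind that dose and the chance of recommending a level that is too toxic.

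**Working it through.** **The plan's own figures (11.1).** Six patients at each of four levels give 24. Adding six pharmacokinetic patients and 20% gives (24 + 6) × 1.2 = 36. With twelve per level, (48 + 6) × 1.2 = 64.8, stated as 65. All reproduce. They are maxima and do not promise six patients at every level.

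**Precision.** The exact one-sided 95% upper bound after 0/n is 1 − 0.05^(1/n). After 1/6 it solves (1−p)^6 + 6p(1−p)^5 = 0.05.

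| Result | Upper bound on DLT rate |
|---|---|
| 0/3 | 63.2% |
| 0/4 | 52.7% |
| 0/5 | 45.1% |
| 0/6 | 39.3% |
| 1/6 | 58.2% |

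A six-patient rule would accept 1/6. Its bound is looser than those of 0/4 and 0/5, and 5 points tighter than that of 0/3. The contrast of 63% with 39% holds only against 0/6.

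**Acceptance of the top level if data are never pending.** This is the setting in which the current rule stops earliest. With q = 1 − p, the current rule accepts on 0/3, or on one DLT in the first three and none in the next three: q³ + 3pq⁵. A six-patient rule accepts with q⁶ + 6pq⁵. At p = 0.4: 0.216 + 0.093 = 0.309, against 0.047 + 0.187 = 0.233.

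**Acceptance at the stated accrual.** Section 11.1 gives 1–2 patients a month. Assumptions: exponential gaps between patients, a 28-day window, DLT times uniform within it. The fourth patient arrives more than 28 days after the third with probability exp(−28/30.44) = 0.40 at one a month and exp(−56/30.44) = 0.16 at two. Simulating the 11.3 table at the top level gives:

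| True DLT rate | Never pending | 1/month | 2/month | Six required |
|---|---|---|---|---|
| 20% | 70.9% | 68% | 67% | 65.5% |
| 1/3 | 42.8% | 39% | 37% | 35.1% |
| 40% | 30.9% | 27% | 25% | 23.3% |
| 50% | 17.2% | 14% | 12% | 10.9% |

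**With the pooled rule of 11.2.2.** Suppose six DLT-evaluable expansion patients are added. The dose then stands with at most 2 DLTs in 9, or at most 3 in 12. At 40%, with data never pending, this gives 16.8% against 14.0%. At the stated accrual it is about 16% (1/month) or 15% (2/month) against 14.0%. With three expansion patients and data never pending it is 20.0% against 16.5%.

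**How often the top level is declared on fewer than six.** Given that level 4 is reached, this happens in 35% (1/month) or 17% (2/month) of cases at a true rate of 20%, and in 53% or 27% at 10%. At 40% it is 13% or 6%. Level 4 must first be reached. With assumed DLT rates of 5, 10 and 20% at levels 1–3 and no data pending, that chance is 0.973 × 0.906 × 0.709 = 63%. With 10, 20 and 25% it is 0.906 × 0.709 × 0.600 = 39%. Under the first set, and 20% at level 4, the overall chance is about 0.63 × 0.35 = 22% or 0.63 × 0.17 = 11%.

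**The case for a change.** The strongest case for a change is that it is cheap. Section 11.1 already budgets six patients at each of four levels, so 24, 36 and 65 would stand, and the recommended dose would have the same basis whichever way escalation ends. The expansion cannot be relied on to supply that basis: it may enrol nobody, and it is aimed at pharmacokinetic data in patients under 12. The pooled rule speaks of the MTD, while the footnote speaks of the recommended dose.

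Part of this stands. The dose can rest on three patients, and the expansion does not guarantee six who are evaluable for DLT. A team that wanted more precision at the ceiling could reasonably choose six.

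The rest does not make it a defect. The single-asterisk footnote applies after at least two DLTs at the level above, so the lower level sits next to observed toxicity and closer scrutiny is natural. The double-asterisk footnote, in the rows at issue, applies when no DLT has been seen at the level itself. The difference in wording has little weight, because Sections 1.1.1 and 11.1 treat MTD and recommended dose as one endpoint and 11.1 places the expansion at either. The pooled rule is naturally read to cover both. Filling the six with expansion patients would put a hematologic restriction on a cohort deliberately opened without one.

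**Conclusion.** The concern does not hold. The plan states its rule consistently in table, text and footnotes, breaches no requirement or figure of its own, and follows the rolling-six design it names. Requiring six at the ceiling would be a different trade-off: up to three more children treated at the top level, in exchange for about 1–4 percentage points less acceptance of a level with a 40% DLT rate (about 1–2 points if six expansion patients are pooled), and some loss of acceptance of a tolerable 20% level.

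The simulated sizes rest on exponential arrivals at 1–2 a month, a 28-day window, uniform DLT times, all patients evaluable, and level 4 having been reached. The pooled figures also assume that the optional expansion enrols the stated number of DLT-evaluable patients. If it enrols nobody, the unpooled figures apply, with an upper limit of 31% against 23% at a true rate of 40% when data are never pending.

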## 11.4 Inclusion of Children, Women and Minorities

The study is open to all participants regardless of gender or ethnicity. Review of accrual to past COG studies of new agents demonstrates the accrual of both genders and all NIH-identified ethnicities to such studies. Efforts will be made to extend the accrual to a representative population, but in a Phase 1 trial which will accrue a limited number of patients, a balance must be struck between patient safety considerations and limitations on the number of individuals exposed to potentially toxic or ineffective treatments on the one hand and the need to explore gender, racial, and ethnic aspects of clinical research on the other. If differences in outcome that correlate to gender, racial, or ethnic identity are noted, accrual may be expanded or additional studies may be performed to investigate those differences more fully.

Racial		Ethnic C			
Categories	Not His La	panic or tino	Hispanic	or Latino	Total
	Female	Male	Female	Male	
American Indian/ Alaska Native	0	0	0	0	0
Asian	2	2	0	0	4
Native Hawaiian or Other Pacific Islander	0	0	0	0	0
Black or African American	4	7	0	0	11
White	16	26	4	3	49
More Than One Race	1	0	0	0	1
Total	23	35	4	3	65

The gender and minority distribution of the study population is projected to be:

THIS PROTOCOL IS FOR RESEARCH PURPOSES ONLY, SEE PAGE 1 FOR USAGE POLICY

PHS 398 / PHS 2590 (Rev. 08/12 Approved Through 8/31/2015)

OMB No. 0925-0001/0002

## 11.5 Pharmacokinetic and Correlative Studies and Response Analysis

A descriptive analysis of pharmacokinetic (PK) parameters of LY2606368 will be performed to define systemic exposure, drug clearance, and other pharmacokinetic parameters. The PK parameters will be summarized with simple summary statistics, including means, medians, ranges, and standard deviations (if numbers and distribution permit).

While the primary aim of this study is to evaluate the toxicity of LY2606368, patients will have disease evaluations performed as indicated in Section 8.1. Disease response will be assessed according to RECIST criteria for patients with solid tumors, and will be reported descriptively.

All these analyses will be descriptive and exploratory and hypotheses generating in nature.

<sup>1These distributions are based on historical Phase 1 enrollments.

```
NCI Pediatric Early Phase
Clinical Trials Network
```

A program funded by the National Cancer

This protocol is for research purposes only, see page 1 for usage policy

# 12.0 EVALUATION CRITERIA

# 12.1 Common Terminology Criteria for Adverse Events (CTCAE)

The descriptions and grading scales found in the revised NCI Common Terminology Criteria for Adverse Events (CTCAE) version 5.0 will be utilized for AE reporting. All appropriate treatment areas should have access to a copy of the CTCAE version 5.0. A copy of the CTCAE version 5.0 can be downloaded from the CTEP website (http://ctep.cancer.gov/protocolDevelopment/electronic applications/ctc.htm).

# 12.2 **Response Criteria for Patients with Solid Tumors**

See the table in Section 8.0 for the schedule of tumor evaluations. In addition to the scheduled scans, a confirmatory scan should be obtained on the next consecutive cycle following initial documentation of objective response.

Response and progression will be evaluated in this study using the revised Response Evaluation Criteria in Solid Tumors (RECIST) guideline (version 1.1). Key points are that 5 target lesions are identified and that changes in the *largest* diameter (unidimensional measurement) of the tumor lesions but the *shortest* diameter of malignant lymph nodes are used in the RECIST v 1.1 criteria.

# 12.2.1 Definitions

- 12.2.1.1 Evaluable for objective response: Patients who exhibit objective disease progression prior to the end of cycle 1 will be considered evaluable for response. For all other patients, only those patients who have measurable disease present at baseline, have received at least one cycle of therapy, and have had their disease re-evaluated will be considered evaluable for response.
- 12.2.1.2 Evaluable Non-Target Disease Response: Patients who have lesions present at baseline that are evaluable but do not meet the definitions of measurable disease, have received at least one cycle of therapy, and have had their disease re-evaluated will be considered evaluable for non-target disease. The response assessment is based on the presence, absence, or unequivocal progression of the lesions.

# 12.2.2 Disease Parameters

- 12.2.2.1 Measurable disease: Measurable lesions are defined as those that can be accurately measured in at least one dimension (longest diameter to be recorded) as  $\geq 20$  mm by chest x-ray, as  $\geq 10$  mm with CT scan, or  $\geq 10$  mm with calipers by clinical exam. All tumor measurements must be recorded in millimeters (or decimal fractions of centimeters).
  - Note: Tumor lesions that are situated in a previously irradiated area must show definitive evidence of progression to be considered measurable.
- 12.2.2.2 Malignant lymph nodes: To be considered pathologically enlarged and measurable, a lymph node must be  $\geq$  15 mm in short axis when assessed

institute of the National Institutes of Health

THIS PROTOCOL IS FOR RESEARCH PURPOSES ONLY, SEE PAGE 1 FOR USAGE POLICY

by CT scan (CT scan slice thickness no greater than 5 mm). At baseline and in follow-up, only the short axis will be measured and followed.

- 12.2.2.3 Non-measurable disease: All other lesions (or sites of disease), including small lesions (longest diameter < 10 mm or pathological lymph nodes with  $\geq 10$  to < 15 mm short axis), are considered non-measurable disease. Bone lesions, leptomeningeal disease, ascites, pleural/pericardial effusions, lymphangitis cutis/pulmonitis, inflammatory breast disease, and abdominal masses (not followed by CT or MRI), are considered as non-measurable.
  - Note: Cystic lesions that meet the criteria for radiographically defined simple cysts should not be considered as malignant lesions (neither measurable nor non-measurable) since they are, by definition, simple cysts. 'Cystic lesions' thought to represent cystic metastases can be considered as measurable lesions, if they meet the definition of measurability described above. However, if non-cystic lesions are present in the same patient, these are preferred for selection as target lesions.
- Target lesions: All measurable lesions up to a maximum of 2 lesions per 12.2.2.4 organ and 5 lesions in total, representative of all involved organs, should be identified as target lesions and recorded and measured at baseline. Target lesions should be selected on the basis of their size (lesions with the longest diameter), be representative of all involved organs, but in addition should be those that lend themselves to reproducible repeated measurements. It may be the case that, on occasion, the largest lesion does not lend itself to reproducible measurement in which circumstance the next largest lesion that can be measured reproducibly should be selected. A sum of the diameters (longest for non-nodal lesions, short axis for nodal lesions) for all target lesions will be calculated and reported as the baseline sum diameters. If lymph nodes are to be included in the sum, then only the short axis is added into the sum. The baseline sum diameters will be used as reference to further characterize any objective tumor regression in the measurable dimension of the disease.
- 12.2.2.5 Non-target lesions: All other lesions (or sites of disease) including any measurable lesions over and above the 5 target lesions should be identified as non-target lesions and should also be recorded at baseline. Measurements of these lesions are not required, but the presence, absence, or in rare cases unequivocal progression of each should be noted throughout follow-up.

